3. STUDY OBJECTIVES AND ENDPOINTS

3.1. Study Objectives

3.1.1. Primary Objective

The primary objective of the study is to evaluate safety and tolerability of 3 intrathecal doses of NurOwn® (MSC-NTF cells).

3.1.2. Secondary Objective

The secondary objectives of the study are:

- To evaluate the efficacy of NurOwn® using improvement in either Timed 25-foot walk (T25FW) speed or 9-Hole Peg Test (9-HPT)
- To evaluate the modulation of cerebrospinal fluid (CSF) and blood biomarkers (neurotrophic factors, neurodegenerative, and inflammatory biomarkers) following NurOwn® transplantation
- To evaluate the efficacy of NurOwn® using:
 - The EDSS
 - The 12 item MS Walking Scale (MSWS-12)
 - Physical function (including average daily step count using ActiGraph's CenterPoint Insight Watch [CPIW] wrist wearable sensor)
 - Low Contrast Letter Acuity (LCLA)
 - Symbol Digit Modality Test (SDMT)
 - MSFC Composite Scores

3.2. Study Endpoints

3.2.1. Primary Endpoints

Primary endpoints of this study are assessment of safety and tolerability by analysis of changes in vital signs and physical and neurological examination findings, hematology, blood chemistry, urinalysis, AEs, SAEs, MRI data and changes in concomitant medications (CM).

3.2.2. Secondary Endpoints

Secondary endpoints for the study are efficacy endpoints with the primary efficacy endpoint evaluated as indicated below:

- Percentage of subjects with improvement from baseline to Week 28 in either T25FW or 9-HPT of $\geq 25\%$.

[Section 9.6](#) provides additional details.

Other secondary efficacy endpoints evaluated include changes from baseline to each post baseline timepoint:

- Percentage of subjects who improve on T25FW by $\geq 25\%$ (Other thresholds such as $\geq 15\%$, $\geq 20\%$ and $\geq 30\%$ will also be evaluated)

BrainStorm Cell Therapeutics Ltd.
Statistical Analysis Plan - Protocol BCT-101-US

April 12, 2019

- Percentage of subjects who improve on 9-HPT by $\geq 25\%$ (Other thresholds such as $\geq 15\%$, $\geq 20\%$ and $\geq 30\%$ will also be evaluated)
- Mean Changes and % Changes in T25FW (ft/sec.)
- Mean Changes and % Changes in 9-HPT (sec.)
- Mean Changes and % Changes in various CSF and blood biomarkers (Biomarkers detailed below)
- Mean Changes and % Changes in EDSS Scores
- Mean Changes and % Changes in EDSS and its Functional System (FS) subscales (Pyramidal, Cerebellar, Brainstem, Sensory, Bowel and Bladder, Visual, Cerebral or Mental, and Ambulation)
- Percentage of Subjects that improve on EDSS by ≥ 1.0 for those with baseline EDSS ≤ 5.5 and improvement ≥ 0.5 for those with baseline EDSS > 5.5 (Note maximum EDSS for subjects enrolled is 6.5 inclusive)
- Mean Changes and % Changes in MSWS-12 Scores
- Percentage of Subjects that improve on MSWS-12 Scores by ≥ 8 points (other thresholds such as improvements of ≥ 7 , ≥ 9 points will also be evaluated)
- Mean Changes and % Changes in Daily Step Count as measured by CPIW
- Mean Changes and % Changes in Step Count as measured by CPIW during T25FW
- Mean Changes and % Changes in count per minute of daily activity as measured by CPIW
- Shift Table on time spent in each of the following categories: (Sedentary, Light, Lifestyle, Moderate, Vigorous, Very Vigorous) as measured by CPIW
- Percentage of time spent in light to vigorous physical activity based on a threshold of > 100 activity counts per minute as measured by CPIW
- Mean Changes and % Changes in LCLA Scores
- Percentage of subjects with an increase in LCLA score by ≥ 7 points (other thresholds such as improvements of ≥ 6 , ≥ 8 points will also be evaluated)
- Mean Changes and % Changes in SDMT Scores
- Percentage of subjects with an increase in SDMT score by ≥ 4 points (other thresholds such as improvements of ≥ 3 , ≥ 5 points will also be evaluated)
- Mean Changes and % Changes in MSFC Composite Z-Scores (25FWT, 9-HPT, SDMT)
- Mean Changes and % Changes in MSFC Composite Z-Scores (25FWT, 9-HPT, SDMT, LCLA)

[Section 9.6](#) provides additional details.

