3.1. INCLUSION CRITERIA

Study participants meeting all of the following criteria will be allowed to enroll in the study:

1. Males and females ages 18 to 65 years old, inclusive, at the Screening Visit
2. Clinical diagnosis of primary or secondary progressive MS (PPMS or SPMS) based on the 2017 revised MacDonald Criteria and have confirmation by the Investigator that the disease has entered the progressive stage at least 6 months prior to enrollment.
3. No evidence of clinical MS relapse or high dose pulse corticosteroid treatment within 6 months prior to screening.
4. Disability status at screening with an Expanded Disability Status Scale (EDSS) 3.0-6.5, inclusive
5. Able to walk 25 feet in 60 seconds or less
6. Stable dose of non-excluded MS Disease Modifying Therapy for at least 6 months prior to Screening Visit (Visit 1).
7. Women of childbearing potential shall either be surgically sterile, or must agree not to become pregnant for the duration of the study. Women must be willing to undergo a serum pregnancy test at screening, and at the conclusion of the study. Participants of childbearing potential must agree to use a medically approved form of birth control (abstinence, intrauterine device (IUD), oral contraception, barrier and spermicide or hormonal implant) throughout the duration of the study and for at least 3 months following the last transplantation. For those women who are sexually active and using oral contraceptives, a second form of barrier contraception is required. Men must be willing to consistently use two forms of contraceptive if their partners are of childbearing age.
8. Capable of providing informed consent and willing and able to follow study procedures, including willingness to undergo multiple/repeated lumbar puncture.

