6.7.3. Change from Baseline

Change from baseline is calculated as (post-baseline result – baseline result).

Percent change from baseline is calculated as (change from baseline/baseline result)*100 as long as baseline is non-zero. If baseline is 0, change from baseline is defined as missing.

If either the baseline or the post-baseline result is missing, the change from baseline and/or percentage change from baseline is set to missing as well.

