Total administration time, for a typical MS patient, is approximately 10–15 minutes to complete, when testing each eye individually and binocular vision for two different contrast levels. The

score for each chart is quantified as the number of letters identified correctly with a maximum score of 70 letters.

Symbol Digit Modalities Test (SDMT)

Mean Changes and % Changes from baseline to each post baseline timepoint in SDMT Scores will be summarized along with other descriptive statistics for continuous variables.

Additional categorical analyses will summarize the number and percentage of subjects with an increase in SDMT scores by ≥ 4 points. A 4 point change in SDMT is considered clinically meaningful⁷. Other thresholds such as improvements of ≥ 3 , ≥ 5 points will also be presented.

The SDMT involves a simple substitution task that normal children and adults can easily perform. Using a reference key, the examinee has 90 seconds to pair specific numbers with given geometric figures.

Total administration time should be approximately 5 minutes.

MSFC Composite Score

Two composite scores will be computed for the MSFC. One composite will include the T25FW, 9-HPT and SDMT and a second composite will include the T25FW, 9-HPT, SDMT and LCLA.

The MSFC Composite Score in the first case is computed as follows:

$$\text{MSFC Score} = \{(\text{Average (1/9-HPT)} - \text{Baseline Mean (1/9-HPT)} / \text{Baseline Std Dev (1/9-HPT)} \\ + \{ - (\text{Average 25-Foot Walk} - \text{Baseline Mean 25-Foot Walk}) / \text{Baseline Std-Dev 25-Foot Walk} \\ + (\text{SDMT} - \text{Baseline Mean SDMT}) / \text{Baseline Std Dev SDMT} \} / 3.0$$

Note: “Average (1/9-HPT)” is the average of the inverse (reciprocal) for the mean time of the two trials on the right hand and reciprocal of the mean time of the two left-hand trials from the test patient, Baseline Mean (1/9-HPT) and Std Dev (1/9-HPT) are the baseline values from each patient in all study groups combined at the baseline assessment;

“Average 25-Foot Walk” is the mean time from the two trials of the 25-foot timed walk; and we take the negative value of the Z-score to make the direction of change the same as the other components. Similarly, the Baseline Mean and Std Dev 25-Foot Walk are of all Baseline Groups combined;

and “SDMT” is the score from the test patient, and the Baseline Mean SDMT and Std Dev SDMT of the combined baseline assessments.

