5.3 MSFC

MSFC-4 score will be derived with LCLA Binocular (both eyes) with 1.25% chart with below formula-

MSFC-4 Score = $\{(\text{Average (1/9-HPT)} - \text{Baseline Mean (1/9-HPT)}) / \text{Baseline Std Dev (1/9-HPT)} + \{ -(\text{Average 25-Foot Walk} - \text{Baseline Mean 25-Foot Walk}) / \text{Baseline Std-Dev 25-Foot Walk}\} + (\text{SDMT} - \text{Baseline Mean SDMT}) / \text{Baseline Std Dev SDMT} + (\text{LCLA-Binocular 1.25\% chart} - \text{Baseline Mean LCLA-Binocular 1.25\% chart}) / \text{Baseline Std Dev LCLA-Binocular 1.25\% chart}\} / 4.0$

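### Percent change is planned for MSFC composite z-scores that are centred on 0, so it has the wrong sign for about half of the patients

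*SAP*

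**What the plan says.** SAP 3.2.2 lists two MSFC endpoints at each post-baseline time point: "Mean Changes and % Changes in MSFC Composite Z-Scores (25FWT, 9-HPT, SDMT") and "Mean Changes and % Changes in MSFC Composite Z-Scores (25FWT, 9-HPT, SDMT, LCLA").

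SAP 6.7.3 gives one percent-change rule for all variables: "Percent change from baseline is calculated as (change from baseline/baseline result)*100 as long as baseline is non-zero". Its only protection of the denominator is for a baseline of exactly zero: "If baseline is 0, change from baseline is defined as missing".

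SAP 9.6 builds the composite as an average of component z-scores. The reference values come from the study's own baseline data. For the walk, the component "is the mean time from the two trials of the 25-foot timed walk", and "the Baseline Mean and Std Dev 25-Foot Walk are of all Baseline Groups combined". The 9-HPT and SDMT are handled the same way. The walk z-score is negated so that a higher composite means better function.

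SAP Appendix I, 5.3, states that "MSFC-4 score will be derived with LCLA Binocular (both eyes) with 1.25% chart" and gives a formula of the same form with four terms. Neither 9.6 nor Appendix I withdraws or redefines the percent change for MSFC.

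**The concern.** Percent change needs a scale with a true zero and baselines that are all positive. A z-score centred on the study's own baseline has neither: its zero is only the average patient at entry. Dividing by a negative baseline reverses the sign of the change, and dividing by a baseline near zero inflates it without limit.

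At stake is the reading of two secondary endpoints. The percent-change row can point the opposite way from the absolute-change row printed beside it, and a reader cannot tell from the table why. SAP 4.3 says the data from these 20 patients are meant to inform a future randomised trial, so a misleading summary could be carried forward.

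**Working it through.** The plan states no figure to reproduce: it gives no MSFC baseline distribution and no expected percent change. The check applies the SAP's formulas directly. The brackets in the 9.6 formula are unbalanced; it is read here as the mean of three z-scores, as Appendix I does for four.

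**Step 1: centring.** For patient *i* and component *j*, z_ij = (x_ij - baseline mean_j) / baseline SD_j, with the sign reversed for walk time. At baseline, the z_ij of each component sum to 0 over patients. The composite C_i, the mean of three or four such terms, therefore also averages 0. Simulation confirmed this to within rounding error. Unless every composite is exactly 0, some baselines must be negative.

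**Step 2: sign and size.** With b the baseline composite and d the change, SAP 6.7.3 gives percent change = 100 × d / b. If b < 0, its sign is opposite to that of d.

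| Baseline | Post | Change d | Direction | Percent change |
|---|---|---|---|---|
| -0.50 | -0.25 | +0.25 | better | -50% |
| +0.50 | +0.25 | -0.25 | worse | -50% |
| -0.50 | -0.75 | -0.25 | worse | +50% |
| +0.50 | +0.75 | +0.25 | better | +50% |
| -0.05 | +0.20 | +0.25 | better | -500% |
| +0.05 | +0.30 | +0.25 | better | +500% |
| +0.02 | +0.27 | +0.25 | better | +1250% |

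The same gain of 0.25 appears as anything from -500% to +1250%.

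**Step 3: how many patients, and what happens to the mean.** The mean baseline is exactly 0 but the median need not be, so the share of negative baselines depends on distribution shape and was simulated with n = 20 (SAP 4.3).

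- *Assumptions not in the documents:* component correlation 0.2 to 0.6; walk time either symmetric or right-skewed (median 8 s, log-SD 0.4 to 1.0); individual change normal with mean 0.3 and SD 0.3, independent of baseline.
- *From the documents:* skewed walk times were limited by the entry criterion in Protocol 3.1, "Able to walk 25 feet in 60 seconds or less".
- *Runs:* 20,000 trials per scenario, for both composites.

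Results:

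- 47% to 50% of patients had a negative baseline, with 7 to 13 of 20 in 95% of trials.
- Mean percent change was negative in 46% to 50% of trials. Mean absolute change was positive in over 99.9%.
- With a gain of 0.1 to 0.5 at correlation 0.4, mean percent change was still negative in 47% to 50% of trials. Mean absolute change was positive in 93% (gain 0.1) to over 99.9% (gain 0.5).
- 9% to 13% of baselines lay within 0.1 of zero.
- At log-SD 0.6 and correlation 0.4, the 95% range of mean percent change was roughly -700% to +750%. Repeat runs moved the lower limit between -662% and -823% and the upper between +742% and +802%.

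A separate simulation gave every patient a gain of exactly 0.25 (4,000 trials per scenario, correlation 0 to 0.6, walk-time log-SD from about 0 to 0.8). Negative baselines were 48% to 50%, and mean percent change was negative in 47% to 51% of trials although every patient had improved.

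**Step 4: after the fix.** With absolute change only, a gain of 0.25 reads +0.25 whatever the baseline, and no signs are reversed.

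**The case against.** The strongest objection is that little depends on these rows. They are two of about twenty descriptive secondary summaries, the valid absolute change sits in the same bullets, and there are no formal stopping rules. SAP 9.6, to which 3.2.2 refers for detail, repeats percent change for EDSS, MSWS-12, LCLA and SDMT but gives only the score formula for MSFC. SAP 9.2 says the z-score transformation will be used to assess change in the MSFC. The percent wording may simply have been carried along. That stands as a limit on severity, but 3.2.2 still plans the summary as written.

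Second, the instability figures concern the mean, whereas SAP 6.4 also requires the median and quartiles. In the scenario with log-SD 0.6 and correlation 0.4, the median percent change is far less extreme: its 95% range is about -36% to +46% for three components and -39% to +46% for four. Its sign is still wrong in 42% and 45% of trials, so it does not rescue the row.

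Third, the simulation fixes the change SD at 0.3 and makes change independent of baseline. Under that assumption, the share of improving patients with a negative percent change (47% to 50%) only restates the share with a negative baseline, and is not extra evidence. The heavy tails also mean that the limits of about 700% to 800% should not be read more finely than that. Both points are accepted; neither touches the algebra.

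Fourth, the zero-baseline sentence in 6.7.3 is a separate editorial matter, and the objection is right that it adds no weight here.

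**Conclusion.** The concern holds, as a minor point. The sign reversal for negative baselines follows from SAP 3.2.2, 6.7.3 and 9.6 with no assumption. That it affects about half of the patients (47% to 50% on average, 7 to 13 of 20 in a single trial) rests on assumed distributions, but it changed little across symmetric and strongly skewed walk times. The group mean percent change is close to a coin toss in sign, and neither it nor the median can be interpreted as a group summary. The primary safety endpoint, the 25% responder endpoint and the absolute MSFC change are unaffected.

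A secondary wording point: the zero-baseline sentence in 6.7.3 follows the percent-change rule and names change where it most likely means percent change. Read literally, it would also discard valid absolute changes where 0 is a real score. Examples are an EDSS functional system grade of 0, which Protocol 15.2.4 allows at EDSS 3.0, and an LCLA chart score of exactly 0. The functional-system shift table in 9.6 would still show those patients, and nothing in the documents says how many would be affected. No bias is claimed.

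**What to change.** 1. In SAP 3.2.2, remove the percent-change part of both MSFC z-score bullets and report absolute z-score change only. Dividing by the absolute value of the baseline is not an adequate substitute: it would correct the sign but leave the instability near zero.
2. In SAP 6.7.3, reword the zero-baseline sentence, for example: *Where the baseline value is 0, only the percent change is set to missing; the absolute change is kept.*

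The cost is an edit to two bullets and one sentence, or one entry in Appendix I, which already corrects a laboratory unit (4.2) and drops a summary that cannot be analysed (the Actigraph section). The tables lose rows, no new data are needed, and nothing valid is lost.

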4. STUDY DESIGN

4.1. Summary of Study Design

This is a proof-of-concept Phase 2 open-label study that will be conducted at multiple study sites in 20 participants with progressive MS with EDSS 3.0-6.5 (inclusive) at the Screening Visit. After providing informed consent and signing a written informed consent document all participants will be observed for a total of 9-10 months (38 weeks).

[figure not shown]
During the up to 10-week pretreatment period patients will be screened and eligibility determined. Approximately 1-4 weeks after the screening visit, bone marrow will be harvested and transferred to the cell manufacturing facility for the isolation and cryopreservation of autologous MSCs.

The first transplantation visit (T1) will occur approximately 6 weeks after the bone marrow aspiration visit (6-10 weeks after screening/enrollment). The subsequent transplantation visits (T2 and T3, at visits 4 and 5) will follow interspaced by approximately 8 weeks (± 14 days) each (Figure 1). The subjects will then be followed for 12 additional weeks after the last transplant visit (T3) at two additional visits, approximately 6 weeks apart.

Assessments and procedures that will be performed during the study are provided in Table 2 and Table 3.

Following the third and last treatment, participants will be followed for two additional monthly visits (through week 28) during which the T25FW, 9HPT and other study outcomes (including an MRI assessment at the End of Study visit) will be obtained, along with vital signs, laboratory tests and recording of CMs and AEs [see schedule of assessments (SOA) in Table 2].

Figure 1 Clinical study flowchart

Clinical study flowchart outlining the pre-treatment and the treatment period and the post-transplant follow-up visits. BMA: Bone Marrow Aspiration; T1, T2 and T3, Transplantation 1, 2 and 3. T- Telephone call visit

4.2. Study Drug

The investigational products for this study will be MSC-NTF cells (NurOwn®).

Participants' bone marrow will be aspirated and MSC cells will be isolated from the total bone marrow mononuclear cell population, propagated in culture and induced to secrete NTFs. NurOwn® (MSC-NTF cells) will then be transplanted back into the participant as follows:

- 100-125 x10⁶ cells by IT administration

NurOwn® will be provided in a ready-to-use subject-personalized unique treatment package with the appropriate primary and secondary labels. The treatment package consists of one 5 mL syringe for IT transplantation. Each treatment package consists of a ready for-injection syringe containing freshly harvested autologous cultured NurOwn® (MSC-NTF cells) at the dose defined in the clinical study protocol.

4.2.1. Bone Marrow Aspiration

A total of 80 to 100 mL of bone marrow will be aspirated from each participant.

4.2.2. Intrathecal Transplant Procedure

Participants will undergo a standard lumbar puncture followed by IT injection of cells. During the procedure, CSF will be collected prior to administration of cells for biomarker analysis.

4.3. Sample Size Considerations

No formal sample size calculation is performed. Efficacy and safety data on 20 subjects will provide information to inform the design of a future randomized clinical study.

4.4. Randomization

Not applicable. This is an open-label, uncontrolled single arm study.

4.5. Clinical Assessments

The schedule of assessments tables below provides an overview of the protocol visits and procedures.

BrainStorm Cell Therapeutics Ltd.
Statistical Analysis Plan - Protocol BCT-101-US

April 12, 2019

Table 2: Schedule of Assessments

Study Period	Pre-treatment period				Cells Transplantation period				Post-transplantation follow-up		
	Visit	V1	V2	V3	V3T	V4	V4T	V5	V5T	V6	V7 ¹¹
Procedure	Screening/ Enrollment	BMA	Cell Transplantatio n (T1)	Telephone Call visit	Cell Transplantation (T2)	Telephone Call visit	Cell Transplantation (T3)	Telephone Call visit	Follow-up visit	End of Study Visi	
Time Schedule	Week -10-6*	Week -5 to - 6	Day 0 - Day 1	Week 1-2	Week 8 (± 14 days)	Week 9-10	Week 16 (± 14 days)	Week 17-18	Week 22 (± 5 days)	Week 28 (± 5 days)	
Informed consent	✓										
Eligibility criteria	✓										
Demographic data	✓										
Height	✓										
Medical History	✓										
MS Medical History ¹	✓										
12 lead ECG	✓										
Neurological Examination	✓									✓	
Viral safety testing (HIV 1 and 2, HBV and HCV)**	✓										
Body weight	✓									✓	
Pregnancy test (for women with childbearing potential)	✓									✓	
Bone marrow aspiration		✓									
Transplant (IT)			✓		✓		✓				
CSF collection			✓		✓		✓				
Visual inspection of injection site			✓		✓		✓				
Blood collection for biomarkers			✓		✓		✓			✓	
Physical examination	✓		✓		✓		✓		✓	✓	
Vital signs ²	✓	✓	✓		✓		✓		✓	✓	
Hematology ³	✓	✓	✓		✓		✓			✓	
Blood biochemistry ⁴	✓		✓		✓		✓			✓	
Coagulation tests ⁵	✓	✓	✓		✓		✓			✓	
Prior/Concomitant medication review	✓	✓	✓	✓	✓	✓	✓	✓	✓	✓	
Adverse events review	✓	✓	✓	✓	✓	✓	✓	✓	✓	✓	
Urinalysis ⁶	✓									✓	
EDSS ⁷	✓		✓		✓		✓		✓	✓	
C-SSRS	✓									✓	
MRI	✓									✓	
Low Contrast Letter Acuity (LCLA)	✓		✓		✓		✓		✓	✓	
MS functional composite ⁸	✓		✓		✓		✓		✓	✓	
SDMT ⁹											
MSWS-12 ¹⁰	✓		✓		✓		✓		✓	✓	
Wearable sensor device issued and training	✓										
Wearable sensor device	✓	✓	✓	✓	✓	✓	✓	✓	✓	✓	

BrainStorm Cell Therapeutics Ltd.
Statistical Analysis Plan - Protocol BCT-101-US

April 12, 2019

Abbreviations: MS=Multiple Sclerosis; EDSS=Expanded Disability Status Scale; CSF=cerebral spinal fluid; C-SSRS=Columbia-Suicide Severity Rating Scale; ECG=electrocardiogram; HIV=human immune deficiency virus; HBV=hepatitis B virus; HCV=hepatitis C virus; IT=intrathecal; V=visit

*Screening Visits scheduling is coordinated with the manufacturing facility

** If applicable must be repeated within up to 7 days prior to BMA

1 MS Medical History to collect type and duration of MS symptoms and Date of Diagnosis

2 Pulse rate, Blood pressure (Respiratory rate, Body temperature)

3 Hematology: Complete blood count (red blood cells with indices, white blood cells with differential and platelet count, hemoglobin, hematocrit)

4 Blood Biochemistry: At V1 and V7: Sodium, potassium, chloride, glucose, BUN, creatinine, bicarbonate, calcium, total bilirubin, AST, ALT, alkaline phosphatase, uric acid, total cholesterol, HDL, LDL. At V3, V4 and V5: sodium, potassium, chloride, glucose, BUN, creatinine

5 Coagulation: PT, PTT, INR.

6 Urinalysis - Specific Gravity, pH, glucose, protein, ketones, blood.

7 EDSS-Expanded Disability Status Scale.

8 MSFC including T25FW and 9-HPT

9 Symbol Digit Modality Test (SDMT).

10 12 item MS Walking Scale (MSWS-12).

11 An Early Termination (ET) visit will be conducted only for participants who discontinue the study after the first treatment, post Visit 3. The ET visit will include all the procedures required at study Visit 7.

BrainStorm Cell Therapeutics Ltd.
Statistical Analysis Plan - Protocol BCT-101-US

April 12, 2019

Table 3: Detailed Schedule of Assessments for Cell Transplantation Visits (V3, V4, and V5)

Estimated Time	xx:00-yy:00	12:00	14:00	20:00	08:00	12:00
Time\ Procedure	Up to 8 hours before transplant	Hr. 0	Hr. 2 (\pm 15 minutes)	Hr. 8 (\pm 15 minutes)	Hr. 20 (\pm 30 minutes)	Discharge/up to Hr. 24
Admit to In-patient Facility	✓					
Physical Examination	✓					✓
Concomitant medication review	✓					✓
Hematology ³	✓					
Blood biochemistry ⁴	✓					
Coagulation ⁵	✓					
Blood collection for biomarkers	✓				✓	
Vital signs ²	✓		✓	✓	✓	✓
Adverse events review ⁶	✓		✓	✓	✓	✓
Cell Transplant IT		✓				
Retention of CSF sample		✓				
Visual inspection of injection site			✓		✓	
Discharge from Inpatient Setting						✓

Abbreviations: BUN = blood urea nitrogen, CSF = cerebrospinal fluid, INR = international normalized ration, IT = intrathecal, PT = prothrombin time, PTT = partial thromboplastin time

*Hematology, biochemistry and coagulation labs are to be drawn and checked before transplant

**To be determined for each study site

1. Hematology: Complete blood count (red blood cells with indices, white blood cells with differential and Platelet count, hemoglobin, hematocrit)
3. Sodium, potassium, chloride, glucose, BUN, creatinine
4. Coagulation - PT, PTT, INR
5. Pulse rate, Blood pressure (Respiratory rate, Body temperature)

